2.9.4.2 Vital signs

Vital sign assessments are performed in order to characterize basic body function. The following parameters were collected: height (cm), weight (kg), pulse rate (beats per minute), systolic and diastolic blood pressure (mmHg).

Data handling

Vital signs collected on treatment will be summarized. Values measured outside of on treatment period will be flagged in the listings.

Data analysis

For analysis of vital signs the clinically notable vital sign criteria are provided in [Table 2-13](#) below.

Table 2-11 Clinically notable changes in vital signs

Vital sign (unit)	Clinically notable criteria	
	above normal value	below normal value
Weight (kg)	increase $> 10\%$ from Baseline	decrease $> 10\%$ from Baseline
Systolic blood pressure (mmHg)	≥ 180 with increase from baseline of ≥ 20	≤ 90 with decrease from baseline of ≥ 20
Diastolic blood pressure (mmHg)	≥ 105 with increase from baseline of ≥ 15	≤ 50 with decrease from baseline of ≥ 15
Pulse rate (bpm)	≥ 100 with increase from baseline of $> 25\%$	≤ 50 with decrease from baseline of $> 25\%$

The number and percentage of subjects with notable vital sign values (high/low) will be presented by treatment arm. Descriptive statistics will be tabulated for baseline, at each post-baseline time point and changes from baseline at each post-baseline time point for each vital sign measure. Figures of change from baseline in systolic and diastolic blood pressure values over time will be displayed via boxplots based on time windows.

A listing of all vital sign assessments will be produced by treatment arm and notable values will be flagged. In the listing, the assessments collected outside of on-treatment period will be flagged.

2.9.4.3 ECOG performance status

The ECOG PS scale ([Table 2-14](#)) will be used to assess physical health of subjects, ranging from 0 (most active) to 5 (least active):

Table 2-12 ECOG Performance Scale

Score	Description
0	Fully active, able to carry on all pre-disease performance without restriction
1	Restricted in physically strenuous activity but ambulatory and able to carry out work of a light or sedentary nature, e.g., light house work, office work
2	Ambulatory and capable of all self-care but unable to carry out any work activities. Up and about more than 50% of waking hours
3	Capable of only limited self-care, confined to bed or chair more than 50% of waking hours
4	Completely disabled. Cannot carry on any self-care. Totally confined to bed or chair
5	Dead

Frequency counts and percentages of subjects in each score category will be provided by treatment arm and time point in subjects of the safety set.

2.10 Pharmacokinetic endpoints

The secondary objective for PK is to to characterize the PK of LAG525, spartalizumab, and carboplatin in the three investigated combinations.

PK parameters

The PK parameters which may be calculated using the PK sampling in cycle 1 and cycle 3, as appropriate, are shown in [Table 2-15](#). The PK parameters are derived based on the non-compartmental methods using Phoenix WinNonlin[®] software version 6.4.

Table 2-13 Non-compartmental PK parameters for LAG525, spartalizumab and carboplatin

AUC _{last}	The AUC from time zero to the last measurable concentration sampling time (t _{last}) (mass x time x volume ⁻¹)
AUC _{0-t}	AUC _{0-t} is the area under the plasma (or serum or blood) concentration-time curve to a defined point in time. For LAG525/spartalizumab AUC _{0-t} = AUC _{0-504h} and for carboplatin AUC _{0-t} = AUC _{0-3h} (amount x time x volume ⁻¹)
C _{min} or C _{trough}	The minimum observed plasma or serum drug concentration (mass x volume ⁻¹)
C _{max}	The maximum (peak) observed plasma, blood, serum, or other body fluid drug concentration after single dose administration (mass x volume ⁻¹)
T _{max}	The time to reach maximum (peak) plasma, blood, serum, or other body fluid drug concentration after single dose administration (time)
Race	Accumulation ratio calculated as AUC _{0-t} on Cycle 3 / AUC _{0-t} on Cycle 1

Descriptive statistics (n, arithmetic mean, CV% mean, standard deviation (SD), median, geometric mean, CV% geo-mean, minimum and maximum) will be presented by treatment for Pharmacokinetic analysis set for all PK parameters defined in [Table 2-15](#) except T_{max}, where only n, median, minimum and maximum will be presented.

All individual PK parameters will be listed by treatment using the Safety set.

PK concentrations

Descriptive statistics (n, m (number of non-zero concentrations), arithmetic mean, CV% mean, SD, median, geometric mean, CV% geo-mean, minimum and maximum) for LAG525, spartalizumab and carboplatin concentration will be presented at each scheduled time point by treatment for the Pharmacokinetic analysis set.

Individual concentration-time profiles for LAG525, spartalizumab and carboplatin concentrations with median will be displayed graphically by treatment for Safety set on the semi-log view. In addition, the mean (+/- SD) and geometric mean concentration-time profiles for LAG525, spartalizumab and carboplatin by treatment over time will be displayed graphically for Pharmacokinetic analysis set on the linear and semi-log view.

All individual plasma concentration data for LAG525, spartalizumab and carboplatin will be listed by treatment for the Safety set.

Handling of PK data below LLOQ or missing

All concentration values below the lower limit of quantitation (LLOQ) (< 0.25 µg/mL for spartalizumab, <5 µg/mL for LAG525, < 1 ng/mL for carboplatin ultrafiltrate and < 100 ng/mL for carboplatin plasma) are set to zero by the Bioanalyst, and will be displayed in the listings as zero and flagged. LLOQ values will be treated as zero in any calculations of summary statistics, and treated as missing for the calculation of the geometric means and their CV%. The number of non-zero concentrations will also be reported in the summary statistics.

Missing values for any PK data will not be imputed and will be treated as missing.

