While the main mechanism of action of platinum agents is believed to be the induction of cancer cell apoptosis as a response to their covalent binding to DNA, recent studies indicated that cellular molecules other than DNA may potentially act as targets, and that part of the antitumor effects of platinum drugs occurs through modulation of the immune system Hato et al 2014. These immunogenic effects include modulation of STAT signaling Lesterhuis et al 2011; induction of an immunogenic type of cancer cell death through exposure of calreticulin and release of ATP and high-mobility group protein box-1 (HMGB-1) Kroemer et al 2013; Tesniere et al 2010; and enhancement of the effector immune response through modulation of programmed death receptor 1-ligand and mannose-6-phosphate receptor expression Liu et al 2010.

The described above immunogenic momentum of platinum chemotherapy is being explored recently in the combination with immune checkpoint blockade. There is a good rationale to combine platinum compounds with checkpoint-blocking antibodies: Platinum can provide immunogenic cell death (ICD) (in case of oxaliplatin or cisplatin based chemoradiation), tumor cell sensitization to CTL lysis, and downregulation of PD-Ls. In several studies conducted in patients with advanced NSCLC, the combination of a checkpoint inhibitor, atezolizumab or pembrolizumab, with platinum-based chemotherapy demonstrated increased efficacy over the chemotherapy alone Lynch et al 2012; Reck et al 2017.

Specific studies to investigate drug-drug interactions (DDI) between LAG525 and/or spartalizumab with carboplatin have not been conducted. Monoclonal antibodies such as spartalizumab and LAG525 are eliminated through protein catabolism and target-mediated disposition, whereas carboplatin is mainly eliminated via the renal route of elimination. Therefore, the potential for drug-drug interaction between the two antibodies and carboplatin is considered low.

Nevertheless, PK of carboplatin, LAG525 and spartalizumab will be characterized in this study, so that DDI, if any, between the combination partners, can be explored (Section 12.5.3). As spartalizumab and LAG525 are intended to be used in combination with chemotherapy, this evaluation is particularly important since chemotherapeutic agents have narrow therapeutic range FDA DDI guidance 2012.

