6.1.1.3 Carboplatin administration

Carboplatin will be administered every three weeks via i.v. infusion over 15 to 60 minutes once LAG525 and spartalizumab infusions are completed. A break of 30 minutes must be observed between any infusions. Any pre-medications should be administered as per local standard practice.

The dose of carboplatin will be adjusted in order to not exceed 900 mg corresponding to a GFR (based on the Calvert formula) capped at 125 mL/min FDA guidance 2010.

Doses subsequent to the initial dose administered at Cycle 1 Day 1 should be adjusted according to the local prescribing information for carboplatin.

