6.5.1 Dose modifications

For participants who do not tolerate the protocol-specified dosing schedule, dose interruptions (LAG525 and spartalizumab and carboplatin) and/or reductions (carboplatin) are either recommended or mandated in order to allow participants to continue the study treatment.

Dose modification recommendations are made for each of the study drugs (for compound specific toxicities). Participants who discontinue a drug of the combination regimens (or two drugs of the triplet) for toxicity and continue on the other drug(s) may remain on study.

The following sections address the specific instructions for mandatory dose modifications and recommended management for adverse events considered suspected to be related to LAG525 and/or spartalizumab and/or carboplatin. These modifications/interruptions must be recorded on the Study Treatment form in EDC system.

The investigators should try to exclude any other etiology and try to identify the most likely drug of the combination to cause the AE.

If the causality of the suspected AE is difficult to determine, the investigator should assume that there is contribution from all drugs (LAG525, spartalizumab, carboplatin).

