Participants receiving spartalizumab and/or LAG525, may experience other irAEs than those listed in this document, therefore all AEs of unknown etiology associated with drug exposure should be evaluated to determine if it is possibly immune-related. In cases where the specific irAE is not listed in the tables below, the investigator should follow the guidance in Section 6.5.1.1. Investigators are encouraged to contact the Sponsor as needed to discuss cases that warrant separate discussion outside of the scope of the current instructions.

The dosing modification requirements are mandatory; however, the AE management guidelines are recommendations and can be modified according to the local practices.

General dose modification instructions:

No changes in dose of spartalizumab and/or LAG525 are allowed.

Overall AEs are to be graded according to NCI-CTCAE v5.0 (https://ctep.cancer.gov). All dose interruptions and the reason for the dose interruption must be documented in the eCRF.

Overall, participants with AEs suspected to be related to spartalizumab or LAG525 including those of potential immune-mediated etiology (irAE) may need to interrupt or permanently discontinue study treatment as outlined in Section 6.5.

Permanently discontinue spartalizumab/LAG525 for any of the following:

- 1. Any life-threatening adverse reaction (excluding endocrinopathies controlled with hormone replacement therapy).
- 2. Inability to reduce corticosteroid dose to 10 mg or less of prednisone or equivalent per day within 12 weeks. The 12 weeks' timeframe will begin from the time the irAE reaches a grade that leads to spartalizumab and or LAG525 interruption.
- 3. Persistent Grade 2 or 3 adverse reactions (excluding endocrinopathies controlled with hormone replacement therapy) that do not recover to Grade 0-1 within 12 weeks after last dose of spartalizumab/LAG525.
- 4. Any severe or Grade 3 treatment-related adverse reaction that recurs.

Table 6-3 Criteria for dose interruption and re-initiation of LAG525 and spartalizumab treatment for potential immune-related diarrhea/colitis

Diarrhea/Colitis (NCI-CTCAE v5.0)		
Grade	Recommended Adverse Event management guidelines	Mandatory Dose Modification requirements
Grade 1 (Increase of <4 stools per day over baseline; mild increase in ostomy output compared to baseline)	Symptomatic treatment (loperamide, hydration, diet) Monitor closely	May continue spartalizumab/LAG525 treatment

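### The carboplatin accumulation ratio in SAP 2.10 has no dose term, so for a participant whose target AUC is reduced it mixes the dose change with pharmacokinetics

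*SAP*

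**What the plan says.** SAP 2.10 introduces its parameters as "The PK parameters which may be calculated using the PK sampling in cycle 1 and cycle 3, as appropriate", in a table titled "Non-compartmental PK parameters for LAG525, spartalizumab and carboplatin". The last row is the ratio: "Accumulation ratio calculated as" AUC0-t on cycle 3 divided by AUC0-t on cycle 1. The same table sets AUC0-t to AUC0-504h for the antibodies and AUC0-3h for carboplatin. The formula contains no dose, and no rule covers a dose that differs between the two cycles. Parameters are summarised by treatment on the pharmacokinetic analysis set and listed individually on the Safety Set. Protocol Table 12-1 does not contain the ratio, so the SAP is its only definition.

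The dosing rules differ by drug:

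- **Antibodies** (Protocol 6.5.1.2): "No changes in dose of spartalizumab and/or LAG525 are allowed".
- **Carboplatin** (Protocol 6.5.1): for participants who do not tolerate the schedule, interruptions "and/or reductions (carboplatin) are either recommended or mandated".
- **Carboplatin** (Protocol 6.1.1.3): "Doses subsequent to the initial dose administered at Cycle 1 Day 1 should be adjusted according to the local prescribing information for carboplatin".

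Protocol 4.3 gives the purpose of measuring all three drugs: "so that DDI, if any, between the combination partners, can be explored".

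**The concern.** An accumulation ratio is read as a statement about the drug: how exposure after repeated dosing compares with exposure after the first dose. That reading needs the same dose in numerator and denominator. It holds for LAG525 and spartalizumab, which are given at a fixed dose. It does not hold for a participant whose carboplatin target AUC is lowered between cycles 1 and 3. There the ratio falls because less drug was given, and the table has nothing that separates this from a change in clearance. A real rise in exposure per mg can be cancelled in the same way.

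The plan expects such participants. Both carboplatin worked examples in SAP 2.4.1 have a lower third dose. What is at stake is how one descriptive carboplatin parameter is read, in a trial that measures carboplatin partly to look for interactions.

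**Working it through.** **Inputs.** SAP 2.4.1 gives two carboplatin dosing examples, written for the dose-intensity calculation:

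- Example 1: administered AUC 6, 6, 5 (800, 800, 650 mg).
- Example 2: administered AUC 5.9, 5.9, 5 (900, 900, 750 mg).

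Neither document states a value for the ratio itself.

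**Reproducing the plan's figure.** Example 1: 6 + 6 + 5 = 17 AUC; 17/18 = 94.4%, as the SAP states. (In Example 2 the listed doses sum to 16.8, not the stated 15.8. This does not affect the ratio below.)

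**Assumptions.** Measured exposure is proportional to dose, clearance is unchanged, nothing carries over between cycles, and infusion time is the same in both. Then

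raw ratio = AUC0-3h(C3) / AUC0-3h(C1) = dose(C3) / dose(C1),

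and the dose-normalised ratio, [AUC(C3)/dose(C3)] / [AUC(C1)/dose(C1)], is 1.00.

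| Case | Raw ratio | Normalised |
|---|---|---|
| Example 1, AUC units: 5/6 | 0.83 | 1.00 |
| Example 1, mg: 650/800 | 0.81 | 1.00 |
| Example 2, AUC units: 5/5.9 | 0.85 | 1.00 |
| Example 2, mg: 750/900 | 0.83 | 1.00 |
| Target AUC 6 to 4: 4/6 | 0.67 | 1.00 |
| 15% decrease: 5.1/6 | 0.85 | 1.00 |

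The last row matters because SAP 2.4.1 counts a carboplatin reduction only when the prescribed AUC falls by more than 15%. A ratio of 0.85 can therefore come from a participant not counted as reduced.

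**Masking.** A true 1.2-fold rise combined with a 6-to-5 reduction gives 1.2 × 5/6 = 1.00.

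**Group level.** If a share f goes from 6 to 5 and the rest are unchanged, the geometric mean is (5/6)^f. The documents give no f; assumed values are:

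- f = 10%: 0.98
- f = 25%: 0.96
- f = 50%: 0.91

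**Limit of mg-normalisation.** SAP 2.4.1 uses Calvert's formula, mg = target AUC × (GFR + 25). Suppose GFR falls from 100 to 80 mL/min (illustrative) and the target stays at 6. The dose goes from 6 × 125 = 750 mg to 6 × 105 = 630 mg. Exposure is held at target, so the raw ratio stays at 1.00. The mg-normalised ratio is 750/630 = 1.19, which is the fall in clearance. Neither ratio alone serves every kind of dose change.

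**The case against.** Several counter-arguments have weight.

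- **The dose aims at a target exposure.** When mg is recalculated for a changed GFR at the same target, the raw ratio is the steadier of the two, as shown above. This stands. A reader might infer that any change in mg distorts the raw ratio; the dosing method does not support that. The problem is confined to changes in target AUC.
- **Some handling exists.** Parameters are to be calculated as appropriate. SAP 2.2 also makes a carboplatin concentration evaluable only after a planned dose, which SAP 2.4.1 describes as AUC 6 in general. On a strict reading, samples after a reduced dose drop out. But SAP 2.2 does not say whether a reduced dose counts as planned, one evaluable concentration is enough for set membership, nothing removes the ratio after a dose change, and the individual listings use the Safety Set. All doses are listed by subject with reasons for change, so a low ratio can be traced by hand. This softens the gap without closing it.
- **The interaction question is only exploratory.** A reader might infer that unequal reductions in Arms 2 and 3 would be reported as a spartalizumab effect on carboplatin. The documents do not support going that far. The visible plan is descriptive, with no PK contrast between arms, and Protocol 12.5.3 summarises cycle 1 by arm as well as cycle 3. Cycle 1 values precede any reduction for toxicity. Part of SAP 2.11 is blacked out, so nothing is claimed about analyses there.
- **Infusion length.** Protocol 6.1.1.3 says "Carboplatin will be administered every three weeks via i.v. infusion over 15 to 60 minutes", so a fixed 3-hour window might seem to need changing too. In an assumed one-compartment model (half-life 1 to 3 h, same dose), 60 against 15 minutes gives an AUC0-3h ratio of 0.95 to 0.90. Running the window to 3 h after end of infusion gives 1.03 to 1.08, so the artefact only changes sign. AUClast, already in the table, runs to the last scheduled sample. Nothing in the documents suggests that infusion time shifts this much within a participant.

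**Conclusion.** The concern holds in a limited form. For carboplatin, the accumulation ratio in SAP 2.10 mixes dose with pharmacokinetics in any participant whose target AUC differs between cycles 1 and 3. Under proportional exposure and unchanged clearance, the affected participant shows 0.81 to 0.85 in the SAP's own examples and 0.67 for a step from 6 to 4, where 1.00 is correct. The effect on the group summary cannot be fixed from the documents; over the assumed shares of 10% to 50% it runs from 0.98 to 0.91.

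The LAG525 and spartalizumab ratios are sound as defined. The matter is minor: the parameter is secondary and descriptive, and it enters no efficacy criterion or decision rule.

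**What to change.** In SAP 2.10, for carboplatin only, keep the raw ratio and add two versions beside it:

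1. A dose-normalised ratio, (AUC/administered mg in cycle 3) / (AUC/administered mg in cycle 1), with a statement that it also reflects any change in renal clearance when mg is recalculated for GFR.
2. The raw ratio restricted to participants with the same target AUC in both cycles. Define this from the prescribed AUC with a stated tolerance, because the SAP's reduction count misses decreases of up to 15%.

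Leave the antibody ratios and the AUC windows as they are.

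The cost is a short SAP text change, one extra derivation, one subset and a few more descriptive rows. Administered mg is already recorded (Protocol 6.1) and already used in the SAP's exposure calculations. The restricted version will rest on fewer participants, so its number should be shown.

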8.5.1.1.2 Analytical method

The validated analytical method for the quantification of LAG525 in human serum consists of trypsin digestion and solid phase extraction as sample clean-up. Prior to mass spectrometric detection, a reverse phase liquid chromatography step is incorporated to reduce sample complexity. The triple quadrupole mass spectrometer is set-up in tandem mode. LAG525 is quantified via detection on of a surrogate peptide. Using a sample volume of 50 μ L of human serum, the validated LC-MS/MS LAG525 assay has an estimated LLOQ of 0.25 μ g/mL.

Spartalizumab (PDR001) is quantified in human serum using a sample preparation method consisting of protein precipitation and tryptic digestion. The assay consists of a reduced phase liquid chromatography step prior to triple quadrupole mass spectrometry detection. Spartalizumab is quantified via detection on of a surrogate peptide. The validated method has an estimated LLOQ of 0.25 $\mu g/mL$, using 25 μL of human serum.

Carboplatin is measured via an Inductively Coupled Plasma Mass Spectrometer using the ratio response of platinium (Pt) to its internal standard. Carboplatin is measured both in ultrafiltrate (estimated LLOQ 1 ng/mL) and plasma (estimated LLOQ 100 ng/mL).

Page 103 of 185 Protocol No. CLAG525B2101 Novartis Confidential Amended Protocol Version 04 (Clean)

Page 106 of 185 Protocol No. CLAG525B2101

9 Study discontinuation and completion

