2.11.1 Immunogenicity

2.11.1.1 Sample ADA Status

Each IG sample is assessed in a three tiered anti-drug anti-body (ADA) testing approach. All IG samples are analyzed in the initial screening assay (first tier). Samples testing negative in the screening assay are not subject to a confirmatory assay. Samples testing positive in the screening assay are then subjected to the confirmatory assay to demonstrate that ADA are

specific for the therapeutic protein product (second tier). The titer of confirmatory positive samples will be subsequently determined in the titration assay (third tier). Samples identified as positive in the confirmatory assay are considered ADA positive and are further characterized in the neutralization assay to indicate the presence of neutralizing antibodies (NAb). Samples can test negative in either the screening or confirmatory assay but for analysis purposes they are not differentiated. The following properties of each sample will be provided in the source data:

- Result of assay according to pre-specified confirmatory cut point: ADA positive (yes) or ADA negative (no)
- Titer (for positive samples): numerical representation of the magnitude of ADA response
- Drug tolerance level: highest drug concentration that does not interfere in the ADA detection method
- Fold titer change (i.e. x-fold): threshold for determining treatment boosted

Determinant samples are defined as samples which are not unevaluable (where unevaluable = sample where assay is not available).

The following definitions apply only to determinant samples:

- *ADA-negative sample*: Determinant sample where assay is ADA negative and respective drug (i.e. LAG525 or spartalizumab) PK concentration at the time of IG sample collection is less than the drug tolerance level.
- *ADA-positive sample*: Determinant sample where assay is ADA positive.
- *ADA-inconclusive sample*: Sample where assay is ADA negative and LAG525 (PDR001) PK concentration at the time of IG sample collection is greater than or equal to the drug tolerance level or missing.

The following definitions apply only to post-baseline ADA-positive samples with a corresponding determinant baseline sample. To be classified as *treatment-boasted* or *treatment-unaaffected*, both the post-baseline and baseline titer must be non-missing:

- *treatment-induced ADA-positive sample*: ADA-positive sample post-baseline with ADA-negative sample at baseline.

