- *treatment-boasted ADA-positive sample*: ADA-positive sample post-baseline with titer that is at least *the fold titer change* greater than the ADA-positive baseline titer.
- *treatment-unaaffected ADA-positive sample*: ADA-positive sample post-baseline with titer that is less than *the fold titer change* greater than the ADA-positive baseline titer.

NOTE: PK concentrations which are flagged for exclusion will still be used to determine ADA-inconclusive and ADA-negative samples.

The following summaries of ADA sample status (n and %) will be provided using *Immunogenicity prevalence set*:

- ADA-positive samples (i.e. ADA prevalence) and ADA-positive NAb samples, both overall and by time point (including baseline). For summaries by time point, the denominator is the number of subjects at that time point with a determinant sample.

Listings will be provided of sample ADA status (including titer for positive samples).

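### The SAP and the protocol give LAG525 quantitation limits that differ 20-fold (5 versus 0.25 µg/mL), and no change is declared

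*SAP*

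**What the plan says.** **Quantitation limits.** Protocol 8.5.1.1.2 (Analytical method) states that "the validated LC-MS/MS LAG525 assay has an estimated LLOQ of 0.25" µg/mL. SAP 2.10, in the rule for data below the LLOQ, has "<5 µg/mL for LAG525". The other limits match. Both documents give 0.25 µg/mL for spartalizumab. For carboplatin the protocol gives "ultrafiltrate (estimated LLOQ 1 ng/mL) and plasma (estimated LLOQ 100 ng/mL"), and the SAP repeats both figures.

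**What happens below the limit.** According to SAP 2.10, such values "are set to zero by the Bioanalyst, and will be displayed in the listings as zero and flagged". They count as zero in the other summary statistics and are "treated as missing for the calculation of the geometric means and their CV". Protocol 12.5.3 and 12.5.3.1 have the same rule, so only the threshold is in dispute. AUClast runs to the last measurable concentration.

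**Link to ADA status.** SAP 2.11.1.1 calls an assay-negative sample ADA-negative when the "PK concentration at the time of IG sample collection is less than the drug tolerance level". The sample is inconclusive if the concentration is at or above that level, or missing. The level is defined ("Drug tolerance level: highest drug concentration that does not interfere in the ADA detection method") but no value is given. The same section adds that "PK concentrations which are flagged for exclusion will still be used to determine ADA-inconclusive and ADA-negative samples".

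**Declared changes.** The SAP is based on protocol version 04, and its Section 4 (changes to protocol-specified analyses) reads as not applicable. Neither document mentions a change of LAG525 assay.

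**The concern.** One number in an operative data-handling rule conflicts with the description of the assay that produces the data, and LAG525 is the only analyte affected. A programmer working from the SAP and a bioanalyst working from the protocol would treat a LAG525 result of, say, 2 µg/mL differently.

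At stake are two secondary objectives: the pharmacokinetics of LAG525 and its immunogenicity. If values in the disputed band were set to zero, arithmetic means at low-exposure time points would fall, geometric means would rise because the low values drop out, and AUClast could end early. In the ADA rules, a recorded zero lies below any tolerance level, so it can make an assay-negative sample look conclusive when drug was in fact present.

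**Working it through.** There is no derived figure in the plan to reproduce. The check sets the two limits side by side and asks which samples could be affected.

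**1. Size of the conflict.** 5 / 0.25 = 20-fold. In half-lives this is log2(20) = 4.32. At the 17-day terminal half-life in protocol 1.1.3.1.2, it is 4.32 × 17 ≈ 73 days of decline.

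**2. Typical subject.** Inputs from the protocol: 400 mg every 21 days (6.1.1.1) and a 17-day half-life. Assumption not in the documents: one compartment with volume V = 3 to 10 L. Formula: C(t) = (400/V) × 2^(−t/half-life).

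- First trough, t = 21: V = 3 gives 133.3 × 2^(−21/17) = 56.6 µg/mL; V = 10 gives 40 × 2^(−21/17) = 17.0 µg/mL.
- Time to reach 5 µg/mL after one dose: 17 × log2(133.3/5) ≈ 81 days for V = 3; 17 × log2(40/5) = 51 days for V = 10.
- Steady-state trough: 98.5 and 29.5 µg/mL respectively. Time to 5 µg/mL after the last dose is then 21 + 17 × log2(98.5/5) ≈ 94 days and 21 + 17 × log2(29.5/5) ≈ 65 days.

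Troughs drawn on schedule therefore sit well above 5 µg/mL.

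**3. Fast-clearing subject.** With an assumed half-life of 5 days and the same V range, the first trough is 7.3 µg/mL (V = 3) to 2.2 µg/mL (V = 10). Scheduled troughs can then fall in the disputed band.

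**4. Effect on summaries, if 5 µg/mL is imposed on data quantified to 0.25.** Assumption: lognormal concentrations at a time point, with log-SD = √ln(1 + CV²) and CV 60% or 100%. The results below are simulated.

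| True geometric mean (µg/mL) | CV | Share set to zero | Arithmetic mean | Reported geometric mean |
|---|---|---|---|---|
| 20 | 60% | 0.6% | 23.27 → 23.25 | 20.2 |
| 20 | 100% | 4.8% | 28.19 → 28.01 | 21.8 |
| 10 | 60% | 10.5% | 11.64 → 11.22 | 11.2 |
| 10 | 100% | 20.3% | 14.09 → 13.41 | 13.4 |
| 5 | 60% | 50% | 5.82 → 4.13 | 7.8 |
| 5 | 100% | 50% | 7.05 → 5.61 | 9.7 |

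At a geometric mean of 10, the arithmetic mean falls by 0.42/11.64 = 3.6% to 0.68/14.09 = 4.8%.

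**5. ADA status.** Let T be the drug tolerance level. Zeroing changes the call only for an assay-negative sample with T ≤ concentration < 5, so it requires T < 5 µg/mL. Over trial values, a change is possible at T = 0.25, 1 or 2.5 and impossible at 5, 10 or 100 µg/mL. The change runs one way, from inconclusive to negative. Positive samples are classified without reference to concentration, and drug-free baseline samples are unaffected. Under SAP 2.11.1.2, ADA incidence counts treatment-boosted and treatment-induced subjects over the whole incidence set, so it would not move. What could move are the counts of ADA-negative and inconclusive subjects.

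**The case against.** The strongest reply is that zeroing is done at the laboratory, at the laboratory's own limit, before the data reach the statistician. If 0.25 µg/mL governs, the 5 in the SAP may be a slip with no effect on any value. If 5 µg/mL governs, nothing between 0.25 and 5 was quantifiable and nothing is lost. The protocol figure is itself called estimated. The SAP was amended before the close-out report on safety and PK (SAP Section 1), so its figure could be the newer one. This stands. A reader might infer that measurable concentrations are being discarded, but the documents do not show that. It would need someone to apply 5 µg/mL to data quantified to 0.25.

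A reader might also infer that ADA status is being misassigned. That depends on a tolerance level that neither document gives, so it can be neither asserted nor excluded.

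On size, protocol 1.1.3.1.2 reports low to moderate between-participant PK variability, which makes the larger shares in the table less likely. SAP 2.2 accepts post-C1D1 pre-dose samples as evaluable only at 504 ± 24 hours, which keeps late, low troughs out of the evaluable set. Appendix 3 of the protocol (16.3.4.2) puts the end-of-treatment visit within 7 days of the last study treatment. These points hold for typical subjects.

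They do not close the matter. LAG525 may be interrupted for up to 12 weeks (protocol 6.5.1.1). That is 84 days, against the 51 to 94 days computed for a typical subject to reach 5 µg/mL. A participant may also stop LAG525 and continue another study drug (6.5.1), so an end-of-treatment sample can come long after the last LAG525 dose. Concentrations flagged for exclusion still feed the ADA rules, and immunogenicity samples count up to 150 days after the last dose (SAP 2.11.1.2).

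**Conclusion.** The inconsistency is real: the two LAG525 limits differ 20-fold, the difference is undeclared, and the documents do not show which limit is in force. The consequences are conditional. Summaries are distorted only if the protocol assay is in use and the SAP threshold is applied to its results. ADA calls change only if, in addition, the tolerance level is below 5 µg/mL.

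On the stated dose and half-life and the assumed 3 to 10 L volume, typical on-schedule samples are probably unaffected. The risk lies in low-exposure samples: fast clearance, long interruptions and late end-of-treatment draws. The table of effects rests on assumed concentration levels and CVs, because the documents give no LAG525 trough concentrations.

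This is a minor correction. PK and immunogenicity are descriptive secondary outputs, no inferential analysis is planned for the close-out report, and the response-rate endpoint and its efficacy decision are untouched.

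**What to change.** Check the bioanalytical validation report for the LAG525 assay used in this study, then state one LLOQ in both documents.

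- If 0.25 µg/mL stands, replace the 5 µg/mL limit in SAP 2.10 with 0.25 µg/mL, and confirm that the laboratory data were not censored at 5.
- If the assay changed and 5 µg/mL is correct, amend protocol 8.5.1.1.2 and record the change in SAP Section 4.

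It would help to state the LAG525 drug tolerance level in SAP 2.11.1.1 at the same time, since that value decides whether ADA status is touched at all.

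The cost is one figure in one document plus a query to the laboratory. No new data are needed. PK and ADA tables would need rerunning only if values had in fact been censored at 5 µg/mL while the assay quantified lower.
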